Principal Investigator: [name]

IRB Project Title: Granulation tissue at G tube site: treatment with Kenalog vs chemical cauterization with Silver Nitrate vs soap washcloth abrasion

Site(s) where study will be performed: C.S. Mott Children's Hospital

Protocol Version 1.0

IRB approval date: 11/12/2021

NCT02519738

PROTOCOL

Principal Investigator: [name]

IRB Project Title: Granulation tissue at G tube site: treatment with Kenalog vs chemical

cauterization with Silver Nitrate vs soap washcloth abrasion Site(s) where study will be performed: C.S. Mott Children's Hospital

Protocol Version 1.0

1.0 Introduction - Background and Rationale: Hypergranulation tissue surrounding gastrostomy tube sites in pediatric patients is a significant problem. This tissue may cause drainage or bleeding that bothers patients and parents. Numerous methods of treatment are used for treatment of hypergranulation tissue, but no data exists to support one method of treatment over another. We plan to perform a prospective randomized trial of three different therapies (silver nitrate cauterization, topical kenalog, and soapcloth abrasion) to identify the best treatment modality. Steroids topically or by intralesional injection has been used to control granulation or hypertrophied scars/keloid. A pertinent reference pertaining to the use of kenalog are as follows:

Lahiri A, Tsiliboti D and Gaze NR.Experience with difficult keloids. British J of Plastic Surgery. 2001; 54(7):633-635

We will follow the patients via office visit at four and eight weeks after initiation of therapy. Measurements of the granulation tissue and photographs will be obtained pre treatment and at each post treatment visit. In addition parents will be asked to fill out a pre and post treatment survey regarding improvement in symptoms. We plan to enroll 120 patients total with the intention of having 40 participants in each group.

- 2.0 Hypothesis/Key Questions: The aim of this study is to prove that kenalog treatments are equal or superior to conventional cauterization with silver nitrate or use of soapcloth abrasion in reducing granulation tissue which forms following insertion of a feeding gastrostomy tube. We will perform measurements, use photographs and survery parents to answer this question.
- **3.0 Objectives**: Evaluate the use of Kenalog vs Silver nitrate cauterization vs soapcloth abrasion around gastrostomy tube sites to reduce the development of granulation tissue.

We will follow the patients via office visit at four and eight weeks after initiation of therapy. Measurements of the granulation tissue and photographs will be obtained pre treatment and at each post treatment visit. In addition parents will be asked to fill out a pre and post treatment survey regarding improvement in symptoms. We plan to enroll 120 patients total with the intention of having 40 participants in each group.

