4.0 Selection of Patients

- **4.1** *Inclusion Criteria (list):* birth 17 years of age, granulation tissue present around gastrostomy tube site for at least 1 week
- **4.2** Exclusion Criteria (list): allergy to any of the potential medications (silver nitrate or kenalog), Non-english speaking patients will be excluded due to inability to effectively communicate study details, risks and benefits.
- 4.3 Age Range: 0-17 years of age

5.0 Study Methodology:

Prospective, randomized study utilizing children ages birth to 17 years, with granulation tissue present around their gastrostomy tube for at least one week. Patients will be randomized to one of the three treatment groups in equal numbers. Once the inclusion criteria are met, informed consent will be obtained from the parent and randomization will occur. Patients will be randomized to either Kenalog (0.5% ointment three times a day for three weeks) or cauterization with silver nitrate (three times a week for three weeks) or abrasion/washing with a soap washcloth (once daily for three weeks). At the end of the three week period, if granulation tissue is still present, the patients will undergo a rest period of one week, followed by another three week course. These children will be followed at four weeks and eight weeks via clinic visits. At the clinic visits, photographs and measurements will be obtained and parent surveys completed.

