10.0 Statistical Considerations

ANOVA and Chi square tests will be used to evaluate the differences between the three treatment groups. Actual measurements of the granulation site, blinded evaluation of the pictures and analysis of pre and post surveys will be incorporated into the data analysis.

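### Section 2.0 sets out to prove Kenalog 'equal or superior', but Section 10.0 plans only three-group tests of difference, which cannot establish 'equal'

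*Combined protocol and SAP*

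**What the plan says.** The protocol words its purpose in three ways. Section 1.0 wants "to identify the best treatment modality". Section 2.0, the hypothesis section, wants "to prove that kenalog treatments are equal or superior to conventional cauterization with silver nitrate or use of soapcloth abrasion", and adds "We will perform measurements, use photographs and survery parents to answer this question". Section 3.0 says "Evaluate the use of Kenalog vs Silver nitrate cauterization vs soapcloth abrasion".

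Section 10.0 is two sentences long. The first reads "ANOVA and Chi square tests will be used to evaluate the differences between the three treatment groups". The second lists the data: "Actual measurements of the granulation site, blinded evaluation of the pictures and analysis of pre and post surveys will be incorporated into the data analysis".

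On size, Sections 1.0 and 3.0 say "We plan to enroll 120 patients total with the intention of having 40 participants in each group". No section gives a margin, a confidence-interval rule, an equivalence or non-inferiority test, a Kenalog contrast, a significance level, a power, or an expected rate or SD.

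**The concern.** The null hypothesis of ANOVA and of the chi-square test is that the groups do not differ. Rejecting it shows a difference. Failing to reject it shows only that the data did not rule out zero, and they may not rule out a large deficit either. So the 'equal' half of the Section 2.0 hypothesis has no planned analysis that could support it.

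The 'superior' half is only partly served. A global three-group test does not say which arm differs, and Section 10.0 neither plans nor excludes pairwise comparisons. The 'or' between the two comparators also leaves unclear whether Kenalog must succeed against both or against either one.

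At stake is the reading of a null result. An aim worded as proof of 'equal', paired only with tests of difference, invites a non-significant p-value to be reported as equality.

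**Working it through.** **The plan's own figure.** The 120 children (40 per group) cannot be reproduced, because no level, power, effect size, SD, rate or margin is stated. Only the 40 per arm comes from the documents. Everything else below is assumed: a 5% level, all 40 evaluable, a yes/no 'resolved' endpoint for the chi-square, and roughly normal sizes for the ANOVA. The logical point does not depend on these assumptions. They only show how large the gap can be.

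**1. A worked result.** Suppose 24/40 resolve on Kenalog and 30/40 in each other arm.
- Pooled rate = 84/120 = 0.70, so 28 resolved and 12 unresolved are expected per arm.
- Chi-square = 16/28 + 4/28 + 4/28 + 16/12 + 4/12 + 4/12 = 2.857 on 2 df, p = 0.24.
- Kenalog minus either comparator = 0.60 − 0.75 = −0.15.
- SE = √(0.60×0.40/40 + 0.75×0.25/40) = √0.01069 = 0.103.
- 95% CI = −0.15 ± 1.96×0.103, which is −35 to +5 points.

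The test is far from significant, yet each interval admits a deficit of 35 points.

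**2. How often a truly worse Kenalog passes the chi-square.** Three-group Pearson test, 2 df, critical value 5.99, by simulation at 40 per arm, with Kenalog 20 points below both other arms:

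| Kenalog vs each other arm | Non-significant |
|---|---|
| 70% vs 90% | 33% |
| 60% vs 80% | 46% |
| 50% vs 70% | 54% |

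**3. The same for measured size.** Let Kenalog be worse than both other arms by d SD, with no baseline adjustment. The noncentrality is λ = 40 × (4/9 + 1/9 + 1/9) × d² = 26.67 d². The chance of a non-significant ANOVA is the noncentral F(2, 117, λ) probability below the 5% critical value, 3.07.

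| d | λ | Non-significant |
|---|---|---|
| 0.3 | 2.40 | 74% |
| 0.4 | 4.27 | 57% |
| 0.5 | 6.67 | 38% |

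**4. What an 'equal or superior' claim would need.** Take a 20-point margin, which is assumed because the plan gives none. Let Kenalog truly equal both comparators, and require the lower limit of both two-sided 95% Wald intervals to lie above −20 points. Simulated power at 40 per arm is about 29% at a 60% resolution rate, 50% at 80%, and 81% at 90%.

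**The case against.** The strongest defence is that 'equal or superior' is loose clinical wording, and that the working aims are those of Sections 1.0 and 3.0, which the planned tests fit. Most of that stands. The tests of difference are not wrong for this trial, and the mismatch is confined to one half of one sentence. But that sentence is in the hypothesis section and is introduced by 'prove', so the softer aims elsewhere do not replace it.

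Three stronger readings are tempting, and the documents do not support them.
- A reader might infer that the sponsor intends to declare equality from a non-significant test. No section says so.
- A reader might infer that no Kenalog-specific comparison will be made. Section 10.0 is silent and does not exclude one. Even so, pairwise tests of difference would not establish 'equal'.
- A reader might infer that 40 per arm is too few for any non-inferiority claim. That depends on the margin and the rate, neither of which is given. With a 20-point margin and 90% resolution, the simulated power is about 81%.

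It is also fair to say that the endpoint, rates and SD-scale deficits above are hypothetical. They illustrate the problem and say nothing about what this trial will find.

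**Conclusion.** The point holds as a mismatch between hypothesis and analysis. No planned analysis can support 'equal', and nothing in the plan says how a null result will be read. The harm is conditional: it arises only if non-significance is reported as equality. If that happened, then under the stated assumptions a Kenalog truly 20 points worse than both other arms would be called equal in roughly a third to a half of trials (33% to 54%). A Kenalog worse by 0.3 to 0.5 SD in size would be called equal in 74% down to 38%. This should be fixed, because the correction is a few sentences and it decides what the trial can conclude.

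**What to change.** 1. Reword the Section 2.0 aim, for example: 'to estimate the difference in reduction of granulation tissue between Kenalog and silver nitrate, and between Kenalog and soapcloth abrasion, and to test whether Kenalog is superior to each'. This keeps the superiority question and removes the ambiguous 'or'.
2. In Section 10.0, report Kenalog minus silver nitrate and Kenalog minus soapcloth, each with a two-sided 95% confidence interval, alongside the ANOVA or chi-square. State that a non-significant test will not be reported as equality.
3. Keep 'equal or superior' only on two conditions. First, a margin, and whether it must be met against both comparators or either one, are fixed before outcome data are seen. Second, the corresponding confidence intervals must exclude a deficit as large as the margin.

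Steps 1 and 2 need no extra patients or data. Their price is a more modest claim. Step 3 costs more: the sponsor must justify a margin, and at 40 per arm the power to meet it against both comparators may be low, about 29% to 50% for a 20-point margin at 60% to 80% resolution.

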4.0 Selection of Patients

- **4.1** *Inclusion Criteria (list):* birth 17 years of age, granulation tissue present around gastrostomy tube site for at least 1 week
- **4.2** Exclusion Criteria (list): allergy to any of the potential medications (silver nitrate or kenalog), Non-english speaking patients will be excluded due to inability to effectively communicate study details, risks and benefits.
- 4.3 Age Range: 0-17 years of age

5.0 Study Methodology:

Prospective, randomized study utilizing children ages birth to 17 years, with granulation tissue present around their gastrostomy tube for at least one week. Patients will be randomized to one of the three treatment groups in equal numbers. Once the inclusion criteria are met, informed consent will be obtained from the parent and randomization will occur. Patients will be randomized to either Kenalog (0.5% ointment three times a day for three weeks) or cauterization with silver nitrate (three times a week for three weeks) or abrasion/washing with a soap washcloth (once daily for three weeks). At the end of the three week period, if granulation tissue is still present, the patients will undergo a rest period of one week, followed by another three week course. These children will be followed at four weeks and eight weeks via clinic visits. At the clinic visits, photographs and measurements will be obtained and parent surveys completed.

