Rapidly absorbed through skin, repeated exposure may cause skin dryness or cracking. May be harmful if absorbed through skin. The drug used in the concentration for the study has not been shown to be harmful to skin. Education regarding the potential side effects, application and skin care will be given to the parents. May cause damage to organs through prolonged or repeated exposure if swallowed. May cause damage to organs through prolonged or repeated exposure if inhaled. The drug is being used for topical application and will not be near the respiratory tract. Target Organs adrenal glands, bone, muscle, gastrointestinal tract, immune system, eyes, nervous system, skin, female reproductive organs, (embryo/fetus) Signs and Symptoms Chronic: muscle weakness, muscle pain, bone fractures, infection, oedema, headache, difficulty sleeping, vertigo, restlessness, euphoria, mental disturbance, depression, anxiety, mood changes, seizure disorders, nosebleeds, cough, fever, nausea, vomiting, anorexia, gastrointestinal disturbance, sore throat, dry mouth, taste disturbance, speech difficulty, congestion, redness and swelling of eyes, vision changes, facial swelling, skin thinning, acne, redness and swelling of skin, hives, bruising, superficial burning sensation, tingling. Medical conditions aggravated include: Diabetes, Liver disorders, infection, immunodeficiency, hypertension, myasthenia gravis, osteoporosis, peptic ulcer, psychotic disorders, colitis, kidney disorders. These are infrequently seen in children, and mostly seen in adults.

Soapy washcloth: There are no foreseeable risks involved with using soapy washcloth as an arm in this study.

9.2 Benefits:

This study may provide improved knowledge about the best way to treat granulation tissue in the future. In addition, the benefit of treatment of each patient's granulation tissue outweighs the risk of adverse effects of the treatment.

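### Section 4.2 has no rule deferring a child with clinically evident infection at the gastrostomy site, although Section 9.1 lists infection (no site stated) among conditions that Kenalog aggravates

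*Combined protocol and SAP*

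**What the plan says.** **Entry rules.** Section 4.1 asks for age from birth to 17 years and granulation tissue of at least one week's standing. Section 4.2 gives two exclusions. One is medical: "allergy to any of the potential medications (silver nitrate or kenalog"). The other concerns families who do not speak English. Section 5.0 then moves to allocation: "Once the inclusion criteria are met, informed consent will be obtained from the parent and randomization will occur".

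**Treatment and follow-up.** One of three equal arms receives "Kenalog (0.5% ointment three times a day for three weeks"). A second three-week course follows a one-week rest if tissue persists. On visits, Section 3.0 says: "We will follow the patients via office visit at four and eight weeks after initiation of therapy".

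**Risk text.** Under Kenalog, Section 9.1 states: "Medical conditions aggravated include: Diabetes, Liver disorders, infection", and the list continues through further conditions. Infection also appears there among the chronic signs and symptoms. No site is given in either place. The list is followed by "These are infrequently seen in children, and mostly seen in adults". Earlier in the same paragraph the protocol says that the drug, at the strength used in the study, has not been found to damage skin. It also promises instruction for families: "Education regarding the potential side effects, application and skin care will be given to the parents".

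**Contact before treatment.** Section 6.0 recruits inpatients and outpatients who present to the pediatric surgery service for treatment of the granulation tissue. Section 8.0 has consent taken face to face. Section 3.0 adds: "Measurements of the granulation tissue and photographs will be obtained pre treatment and at each post treatment visit".

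**The concern.** The protocol's risk text names infection as something a study drug can aggravate, and the ointment is applied to the gastrostomy site. A reader would expect the entry criteria to deal with a child whose site is visibly infected at screening. They do not.

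What is at stake is the safety of individual children, not the validity of the comparison between arms. Followed as written, the plan allows a full first course of topical steroid to be started and finished on an infected site before any scheduled visit. For an outpatient, parent education is the only safeguard the protocol states for that interval. Entry is therefore the one protocol-defined point at which a clinician can act before the first course is over.

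**Working it through.** The plan gives no figure to reproduce on this point. The check is a reading of the text with a little arithmetic on timing.

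**1. Is there a rule anywhere?** I looked through the whole document for an exclusion, deferral, screening step or stopping rule that concerns infection.

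| Place | What it says about infection |
|---|---|
| 4.1 Inclusion | Nothing |
| 4.2 Exclusion | Nothing; allergy and language only |
| 5.0 Methodology | Nothing; eligibility leads to consent and randomisation |
| 6.0 and 8.0 Recruitment, consent | Nothing |
| 9.1 Kenalog risks | Listed as a chronic sign or symptom and as an aggravated condition, no site given |
| 9.1 Silver nitrate and washcloth risks | Nothing |
| 10.0 Statistics | Nothing |

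Infection appears only in the Kenalog risk text. No entry rule takes it up.

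**2. Chance of Kenalog for such a child.** Inputs from Sections 1.0 and 3.0: 40 per arm, 120 in total. 40/120 = 1/3. This is conditional on the child being enrolled.

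**3. First course against first visit.** Inputs from Sections 3.0 and 5.0.
- Length of course: 3 weeks × 7 = 21 days.
- Applications with full adherence: 3 per day × 21 = 63. At an assumed 75% adherence, 0.75 × 63 ≈ 47; at an assumed 50%, 0.50 × 63 ≈ 32. The documents give no adherence figure.
- First scheduled visit: 4 weeks × 7 = about day 28, roughly a week after the course ends.

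The second course is left out because it begins after the rest week, at about the time of the week-four visit. The count describes exposure only; the documents link no number of applications to harm.

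**4. How many children?** The documents give no rate of site infection at entry and no account of how often the service would defer such a child. Without both, the number exposed cannot be calculated, and I attempt no estimate.

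**5. Does Section 9.1 settle the matter?** The remark on frequency in children bears on how often the problem arises; it does not make an infected child ineligible. The remark on strength concerns skin in general and does not mention an infected site.

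**The case against.** The strongest reply has three parts.

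**The documentary support is thin.** The Section 9.1 list is general hazard text for the drug. It sits beside entries on swallowing and inhalation and includes largely systemic conditions such as hypertension and psychotic disorders. A reader might infer that the protocol itself says this ointment worsens infection at a stoma. It does not; that step is clinical inference, resting on where the ointment is applied. The protocol's only statement on local skin safety at the study strength is reassuring. All of this stands, and it limits the weight of the point. It does not supply the missing rule.

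**A surgical service sees the child first.** Consent is face to face and the site is measured and photographed before treatment. A clinician may well hold back a child with an obviously infected site. A reader might infer from the silence in Section 4.2 that infected children will be enrolled, or might attach a probability to it. The documents support neither, since they give no prevalence and no deferral practice. But measuring and photographing are not an infection assessment, and nothing in the protocol tells the clinician to defer.

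**The remedy relies on the same clinical judgement already available.** True. The gain is that the judgement becomes required, consistent and recorded.

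Two further readings go too far. The plan does not contradict itself: a risk list and a short set of exclusions can coexist. Nor does this point extend to immunodeficiency or the other listed conditions, for which no case is made here.

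**Conclusion.** The point holds as a gap in the entry rules, of minor to moderate severity. As written, a child with clinically evident infection at the gastrostomy site qualifies, and once enrolled has a one-in-three chance of a three-week steroid course on that site that ends before the first scheduled visit. Inpatients, and children with unscheduled contact, may be seen sooner.

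The conclusion rests on two things: the absence of any infection rule in the document, which can be checked directly, and the clinical inference that an unspecified entry for infection is relevant where the ointment is applied. It depends on no assumed infection rate. The number of children affected is unknown, and no probability of exposure or of harm is claimed.

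**What to change.** Add one exclusion to Section 4.2, applied before randomisation and in all three arms: *clinically evident infection at the gastrostomy site as judged by the treating clinician (drainage or bleeding from granulation tissue alone does not count); the child may be re-screened once it resolves.* The clinician records yes or no at the existing pre-treatment encounter.

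The bracketed wording is needed because Section 1.0 notes that granulation tissue can itself drain or bleed; without it the criterion could remove the very children the trial is for. The rule should cover every arm even though Section 9.1 mentions infection only under Kenalog. Applied before allocation and regardless of arm, it leaves the comparison undisturbed. The target of 120 does not change.

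The cost is one line of protocol text, one item on the screening form and a brief inspection at a visit that already takes place. Some children will enter later or not at all. How many is unknown; for scale only, each assumed 1% of entrants deferred is 0.01 × 120 = 1.2 children. Generalisability is slightly narrower, and the criterion relies on clinical judgement.

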6.0 Study Methods

- Source (location) of records or patients to be recruited:: Patients presenting to the Pediatric surgery service at Mott Children's Hospital either as an inpatient or outpatient, for treatment of granulation tissue at their gastrostomy site. The patients and their parents will be interviewed and the prospect of participating in this clinical trial will be discussed with them in a private consultation room where they will have opportunities to question the trial and protocol.
- 6.2 Describe how the charts to be reviewed will be identified: Patients meeting criteria will be identified through department specific queries from case schedules.
- 6.3 Describe who will identify charts to be reviewed: The study team

